3.2 Secondary

The following secondary quantitative outcome measures for the trial will be assessed:

- Percent of youth using antipsychotics at 6 months, measured by prescription fill data available for the 180 day follow up period;
- Total person-months of antipsychotic use by youth, per prescription fill data available for the 180 day follow up period.
- Emergency department/urgent care visit frequency, both for psychiatric crises and for other reasons;
- Percentage of baseline and follow-up safety assessments (i.e., BMI measurement and laboratory results);
- Percentage of clinicians that follow CAP advice according to algorithm;
- Modal stage at departure from algorithm (first line, second line, third line treatment prior to antipsychotic);
- Percentage of patients with change to psychotropic medication treatment plan following second opinion review;
- Percent of patients that agree to behavioral health (BH) navigation;
- Percentage of patients attending two or more system-provided therapy sessions;
- Percentage of patients attending two or more study-provided therapy sessions;
- Of patients in study therapy, percentage who subsequently attend two or more system-provided therapy sessions.

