As these power calculations are based on the assumed percent of participants on any antipsychotic in the control arm and assumed pattern of intervention effects, we provide examples of detectable intervention effects corresponding to alternative scenarios in the table that follows, including varying rates of subgroup prevalence to evaluate power regarding intervention effectiveness in less prevalent minority groups. In summary, at a range of percentages of participants with any antipsychotic use in the control arm, we will have excellent power to detect a variety of clinically meaningful intervention effects within the expected range.

Using an estimated rate of emergency department visits of 0.0325 per month on control(47) and with a one-sided 0.025 alpha level with equal allocation between groups, we estimate 71% power(48) with 400 patients per arm and 67% power with 360 patients per arm (allowing for loss to follow-up) respectively, to detect equality of emergency department visit rates (i.e., a true rate ratio of 1) in a non-inferiority evaluation with a margin of 1.5. With a greater monthly emergency department rate of 0.05, we would have 88% and 84% power with 400 and 360 patients per arm respectively under otherwise equivalent conditions.

Power under varying percentages of participants in each arm taking antipsychotic medication at 6 months (based on medication orders) and under various subgroup prevalence assumptions.

Subgroup prevalence	n per arm*	Intervention	Control	Power
100%	360	89%	95%	80%
100%	360	85%	95%	>99%
100%	360	80%	90%	97%
100%	360	75%	85%	92%
25%	90	82%	95%	80%
18%	65	78%	95%	80%
10%	36	75%	95%	67%
5%	18	65%	95%	62%

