Hypothesis-generating exploratory subgroup analysis will be the Heterogeneity of Treatment Effects (HTE), conducted using adjustment variables in the model. To perform HTE analyses, we will use the same analysis procedure for the primary outcome but now including adjustment variables indicated below separately, with an interaction term between the treatment and the covariate. HTE analyses are prespecified for the same variables as below: provider type (MH vs. non-MH), gender, age, race/ethnicity (composite), new health plan enrollee status, insurance type (Medicaid vs. non-Medicaid) and whether participant had an exclusion diagnosis in year prior to baseline.

Variables	Definition	Present/Absent
person_days	Person-days on AP (orders) during 180 Day Follow-up Period (using orders)	present
group	Randomization Group – use for restricted descriptive stats (Intervention/Control)	present
group_cat	Randomization Group – use in models (Control (0)/Intervention (1))	present
prior_hosp	Prior Hospitalization (No (0)/Yes(1))	present
p_offset	Number of days of follow-up for primary analysis (using orders)	present
provider_type	Provider type of the enrolling provider, based on specialty (Non-Mental Health (0)/Mental Health (1))	present
age_emanicip	Emancipated age according to state (No (0)/Yes(1))	present
gendern	Gender (Male (1)/Female (2))	present
race_white_NH	Race - White non-Hispanic (only) (No (0)/Yes(1))	present
insuranceType	Type of insurance Commercial/Medicaid/Other	present
exclusion	Exclusion diagnosis in year prior to baseline	Needs to be created using baseline dx variables
new_enrollee_1	new health enrollee (1 st definition) Yes/No	present
new_enrollee_2	new health enrollee (2 nd definition) Yes/No	present

Secondary analysis I

Emergency department visit/ Urgent care frequency, both for psychiatric crises and for other reasons

Definition: Number of emergency department visits and urgent care visits that occurred during the study, from the enrollment date to 6 months post-enrollment date

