Inferential analysis: For these analyses, we have data that shows the frequency of emergency visits and frequency of urgent care separately, the outcomes. The main predictor is the treatment arm (intervention or control). We will have one record per patient, which shows the total number of ED or UC visits throughout the study (maximum of 6 months). We will perform Poisson regression analyses, where the outcome is the frequency of ED or UC visits for each enrolled patient and the offset is the number of days follow-up. The treatment arm and inpatient hospitalization in the prior year will be the only covariates included in the regression model, and the estimated coefficient for treatment arm is interpreted as the log-RR of visiting ED or UC more/less frequently, for an intervention patient vs. a control patient. Patient will be the unit of

Analysis plan for Safety Use of Antipsychotics in Youth (SUAY)

analysis for this regression model, and the regression model will be fit using generalized estimating equations (GEE) to account for correlation within provider. We will estimate standard errors using a robust (sandwich) covariance estimation and construct a 95% confidence interval (CI) around the estimated RR. The estimated RR and two-sided confidence interval will be compared to the non-inferiority margin, $M=1.5$, and non-inferiority of the intervention will be concluded if the entire coverage of the 95% CI is less than 1.5.

Variables	Definition	Present/Absent
ed_uc	This is the number of days with emergency department and/or urgent care visits that occurred during the study, from the enrollment date to 6 months post-enrollment	absent
group	Randomization Group – use for restricted descriptive stats (Intervention/Control)	present
group_cat	Randomization Group – use in models (Control (0)/Intervention (1))	present
e_offset	Number of days of follow-up for ED/UC analysis	absent
prior_hosp	Prior Hospitalization (No (0)/Yes(1))	present

Secondary analysis II

Percentage of youth with baseline and follow-up safety assessments (i.e., BMI measurement and laboratory measure/orders)

For these analyses, we will measure safety assessments of BMI and laboratory (Lipids, cholesterol, Hb1ac, prolactin, and any labs (at least 1)) measure/orders:

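### The emergency and urgent care outcome names psychiatric crises and other reasons, but the SAP analyses one pooled count, so a pooled non-inferiority result alone cannot show that psychiatric crises did not rise

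*SAP*

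**What the plan says.** Protocol 3.2 lists the secondary outcome as "Emergency department/urgent care visit frequency, both for psychiatric crises and for other reasons". The SAP's outcome list repeats it, and the heading of Secondary analysis I reads "Emergency department visit/ Urgent care frequency, both for psychiatric crises and for other reasons".

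Below that heading, reason disappears. The definition line is "Number of emergency department visits and urgent care visits that occurred during the study". The analysis text says "we have data that shows the frequency of emergency visits and frequency of urgent care separately, the outcomes", which is a split by setting (ED or urgent care), not by reason. The model uses "one record per patient, which shows the total number of ED or UC visits throughout the study". The variable table has one outcome, ed_uc: "This is the number of days with emergency department and/or urgent care visits that occurred during the study". It is marked as absent from the dataset, as is its offset.

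The decision rule is that "non-inferiority of the intervention will be concluded if the entire coverage of the 95% CI is less than 1.5". Protocol 8.2.1 sets the margin of 1.5 for the ED visit rate overall. It assesses non-inferiority only if superiority is shown on antipsychotic use at 6 months. The SAP section does not repeat that condition.

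**The concern.** Protocol 8.2 compares ED visits between arms to detect unintended harm. The intervention steers prescribers away from an antipsychotic; Protocol 7.1 sets the alert's default to removing the order. Visits for psychiatric crises are an obvious place for harm to appear. If they are a minority of all ED and urgent care visits, a rise in them moves the pooled ratio only a little.

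A reader of the outcome list would expect to learn what happened to psychiatric visits. The SAP followed to the letter reports one all-reason ratio. A pass could then be taken as evidence that psychiatric crises did not rise, which the analysis cannot show. This is separate from the pooling of ED with urgent care: it would remain if only ED visits were counted.

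**Working it through.** **Inputs.** From Protocol 8.2.1: control ED rate 0.0325 per month (alternative 0.05), 400 or 360 patients per arm, one-sided alpha 0.025, margin 1.5. Follow-up is 6 months (Protocol 4). Assumed, because the documents do not give it: the psychiatric share of visits, f = 20%, 30% or 50%.

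**Step 1: reproduce the stated power.** For independent Poisson counts and a Wald test on the log rate ratio, with true ratio 1:

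power = Φ( ln 1.5 / √(2/E) − 1.96 ), where E = n × 6 × rate is the expected number of events per arm.

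- 0.0325 per month, n = 360: E = 70.2, √(2/E) = 0.1688, power 67.1% (stated 67%).
- 0.0325 per month, n = 400: E = 78.0, power 71.6% (stated 71%).
- 0.05 per month: 84.6% and 88.1% (stated 84% and 88%).

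The method matches the plan's own.

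**Step 2: dilution.** If psychiatric visits rise by 50% and other visits do not change, the pooled ratio is R = 1 + f × 0.5. With E₀ = 70.2 control events and E₁ = 70.2 × R:

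SE = √(1/E₀ + 1/E₁); P(upper limit < 1.5) = Φ( ln(1.5/R)/SE − 1.96 ).

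| f | R | E₁ | SE | argument of Φ | P(pooled pass) |
|---|---|---|---|---|---|
| 20% | 1.10 | 77.2 | 0.165 | −0.08 | 47% |
| 30% | 1.15 | 80.7 | 0.163 | −0.33 | 37% |
| 50% | 1.25 | 87.8 | 0.160 | −0.82 | 21% |

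**Step 3: sensitivity.**
- At 0.05 per month: 65%, 52% and 29%.
- Psychiatric visits doubled, at 0.0325 per month: about 28%, 14% and 3%.
- Other-reason visits 10% lower in the intervention arm, psychiatric visits up 50%: for f = 20%, R = 0.2 × 1.5 + 0.8 × 0.9 = 1.02, giving 63%; for 30% and 50%, 51% and 28%.
- Clustering or overdispersion, shown as an assumed variance inflation of 1.5 or 2.0: the 47% falls to about 34% or 26%.

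All these probabilities are conditional on the superiority condition being met.

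**Step 4: precision of a split by reason.** At an observed ratio of 1, with 70.2 × f psychiatric events per arm, the upper 95% limit is exp(1.96 × √(2/(70.2 f))). For f = 20% (14.0 events), 30% (21.1) and 50% (35.1) it is 2.10, 1.83 and 1.60. Power to show non-inferiority at 1.5 for psychiatric visits alone would be about 19%, 26% and 40%.

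**The case against.** The strongest reply is that the outcome's wording describes scope: visits of every kind count. The documents offer support. Protocol 10.1 and 10.1.2 divide hospitalizations into psychiatric and non-psychiatric but leave emergency and urgent care visits undivided in the same lists. The non-inferiority plan in 8.2.1 never separates reasons, and the SAP's definition line counts all visits. A reader might infer that a by-reason outcome was promised and then dropped. The text does not establish that. What stands is that the SAP does not say which reading it intends, and naming the two reasons would add little if pooling were all that was meant.

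A reader might also infer that the documents call a 50% rise in psychiatric visits unacceptable. They do not: that threshold is for the overall ED rate, and the 50% rise in the working is an illustration.

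Nor are psychiatric crises unmonitored. Protocol 8.2 compares suicide attempts, deaths and admissions between arms, and 10.1 and 10.1.2 report suicide attempts and psychiatric hospitalizations to the DSMB. These cover some severe crises, but they are not SAP outcomes and they miss psychiatric visits that end in discharge.

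Finally, an all-reason rate is a legitimate net safety measure. Protocol 2.1 and 2.2 describe serious antipsychotic side effects, so non-psychiatric visits may respond to the intervention as well. That is a reason to keep the pooled test, and also a reason to see the two components.

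**Conclusion.** The point holds as a gap between the named outcome and its analysis. As written, the SAP delivers only a pooled ratio, and a pooled pass does not exclude a material rise in psychiatric visits. Under the plan's own rate and sample size, a 50% psychiatric rise would still pass about 47%, 37% or 21% of the time at assumed shares of 20%, 30% or 50%.

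These figures rest on independent Poisson counts, unchanged other-reason visits, a met superiority condition, and a rate that the protocol gives for ED visits while ed_uc also counts urgent care. Masking is substantial when psychiatric visits are a minority. It is small for a doubling at a 50% share.

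It would go too far to infer that splitting by reason would hold the chance of wrongly clearing a psychiatric rise at the nominal 2.5%. That would need a separate test against a psychiatric margin, which the documents do not set and the trial is not powered for.

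**What to change.** In SAP Secondary analysis I:

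1. Keep the pooled count against 1.5 as the non-inferiority analysis.
2. When ed_uc is built, also derive a psychiatric or self-harm count and an other-reason count, using a stated rule based on the visit diagnosis.
3. Fit the same Poisson GEE, with the same offset, covariates and robust errors, to each count. Report each rate ratio with its 95% interval as an estimate, without a separate non-inferiority test.
4. State that the pooled result alone does not show that psychiatric crises did not rise.
5. If visit reason cannot be obtained, state that the outcome is all-reason only and limit the conclusion to match.

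The cost is SAP wording, a coding rule, two derived counts and two model runs. Visit diagnoses must also be extracted. Nothing in the documents shows that this has been done, and the SAP records that data collection for Secondary analysis VIII was not completed for lack of time. The intervals will be wide, as Step 4 shows, and wider still with clustering. They should be presented as such.

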3 OUTCOME MEASURES

Outcome measures will be collected regardless of the extent to which intervention arm clinicians, patients, or families accepted or utilized interventional components. That is, we will follow an intent-to-treat approach and encouragement trial methods.

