5.2 Patients and Families: Inclusion and Exclusion Criteria for Patient Subjects

Potentially eligible patients are logged for study enrollment at the time the medication alert fires. Patients are assigned to the study arm of the randomized prescribing provider. Local study staff will blindly confirm eligibility via medical record review for all intervention and control arm patients logged for eligibility review and enrollment.

Inclusions:

- Patient is ≥ 3 and < 18 years of age at the time of the encounter at which the study alert fired;
- Study service (BH navigation, bridging therapy, CAP consult) ordered in Epic for the patient;
 - The BPA allows providers to remove the antipsychotic order and still order services.
- Patient is initiating a new episode of outpatient treatment with an antipsychotic medication.
 - New episodes are defined by no record of an antipsychotic medication being ordered within the health system as part of an outpatient care plan in the prior 180 days.

Exclusions:

- Patient has a diagnosed psychotic disorder, mania, autism spectrum disorder, or intellectual disability;

- Patient was enrolled in the SUAY pilot study;
- The antipsychotic entered is prochlorperazine (Comazol®) – which is used to treat nausea;
- An outpatient antipsychotic order is entered by a temporary provider in the health system. For example, a “doc of the day” signing an order initiated by a pharmacist transferring an existing prescription to the health system. This situation may also occur when a temporary provider signs a medication order for a prescription initiated in an inpatient setting as part of a discharge plan.
 - Note that orders placed by temporary providers do not count towards the 180 day medication free period for defining a new episode of care.
- The antipsychotic order was placed within an urgent care, emergency department, or inpatient setting (to avoid intervening during a crisis).
 - Note that orders placed in these settings do not count towards the 180 day medication free period for defining a new episode of care.
- Primary language is not English (e.g., patient requires a translator).

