6 CONTROL ARM

The control arm advance communication and medication alert inform the prescriber of *Choosing Wisely*® recommendations regarding antipsychotic medications in children and adolescents. These guidelines were developed by the American Psychiatric Association (APA). Available at: <http://www.choosingwisely.org/clinician-lists/american-psychiatric-association-antipsychotics-in-children-or-adolescents/>

The firing of the control arm medication alert will add the patient to the study enrollment log as a comparison case. Study staff will confirm eligibility via blinded chart review for all patients logged.

The follow up period is 6 months.

Should a control arm provider find SUAY orders in Epic and attempt to order a study service (e.g., navigation, expedited access to bridging therapy), an alert will fire to inform him/her that the patient is not eligible for the service.

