7 INTERVENTION ARM

7.1 Intervention Arm Medication Alert Intervention Description

Randomized providers at each site will be informed in advance of the quality improvement study being conducted. The communication will inform intervention arm providers of the nature of the interventional components (e.g., medication alert, case review by a child and adolescent psychiatrist, behavioral health navigation, bridging therapy).

The medication alert is triggered by entering an antipsychotic in Epic for a target patient. See Appendix B. The patient is added to a study enrollment log at the time of the encounter. The intervention arm medication alert links providers to a document containing *Choosing Wisely*[®] guidelines, the national expert consensus panel clinical guidelines developed for SUAY, and contextual study information.

Within the alert, the prescriber has the option to:

- keep/remove the medication entered (default = remove)
- keep/remove an order for a provider-to-provider consult with the CAP (default = keep)
- keep/remove an order for BH navigation for the patient (default = keep)
- keep/remove an order for expedited access to bridging therapy for the patient (default = keep)

The study CAP is automatically notified that a review is needed each time an intervention arm provider actively orders a CAP review in the alert and after a patient is verified eligible when a consult is not actively ordered.

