APPENDIX A: SCHEDULE OF EVENTS

Event	Description	Timing
Medication Alert and Enrollment Log Entry	The medication alerts fire in Epic during routine clinical encounters at which an antipsychotic is entered in Epic for a target patient. The patient is automatically added to the study enrollment log when the alert fires.	Day 0
Alternatively: Active Order Entered in Epic and Enrollment Log Entry	The intervention arm provider directly orders a study service (i.e., navigation, bridging therapy, CAP consult) in Epic outside of the medication alert. The patient is automatically added to the study enrollment log when the order is entered.	Day 0
Eligibility Validation	Study eligibility will be validated by chart review for all patients logged.	Target: Day 0-3
Child and Adolescent Psychiatrist Review and Recommendations	The study CAP will complete case reviews and send the prescriber recommendations within 3 business days of receiving notification of an eligible case. Consultation will be scheduled to occur within 10 business day when the study CAP requires more information and a consult wasn't ordered.	Target: Day 0-6 (review only or consult ordered) Target: Day 0-13 (consult not ordered, discussion needed)
Behavioral Health Navigator Outreach to Prescriber	The BH navigator will outreach the prescriber following CAP review. The navigator will also send periodic clinically relevant updates while his/her patient is receiving behavioral health navigation support.	Target: Day 3-180 (i.e., after the CAP's review is completed)
Behavioral Health Navigation for Patient/Teen	The navigator will contact families/teens to offer up to 6 months of BH navigation. Outreach will occur within 2 business days following CAP review. Teens/families accepting this extra support will be contacted at least monthly. Ad hoc contacts may be made if psychotherapy appointments are missed and not rescheduled.	Target: Day 6-180 (i.e., after BNH outreach to provider is complete)
Bridging Therapy	Some teens/families will be offered bridging sessions with a study therapist. Up to 9 sessions may be offered.	(variable)

6 Month Follow Up Period	Data will be collected for the 6 month period after each eligible patient is added to the enrollment log. Analytic data will be derived from the EMR and other health plan data systems and study tracking systems.	Day 0-180
--------------------------	---	-----------

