Definition I: BMI/laboratory measure/orders at baseline is defined as BMI/laboratory measure/orders observed in the 90 days before randomization and 7 days after randomization. BMI/laboratory during follow-up is defined as any BMI/laboratory measure/orders observed at least 30 days to +181 days following the randomization date. If no AP orders were made on the randomization date then these variables should be NA. The main predictor is the treatment arm (intervention or control). For these analyses, we will exclude those that did not have an AP order on randomization date.

We will perform 3 logistic regression analysis, where the outcome is a binary indicator of

- i. BMI/Laboratory measure/orders entered at baseline (yes/no)
- ii. BMI/Laboratory measure/orders entered at follow-up (yes/no)
- iii. BMI/Laboratory measure/orders entered at baseline and follow-up (yes/no)

For these analyses, we will exclude those that did not have an AP order on randomization date.

Descriptive analysis will summarize **the percent of patients with observed BMI/Laboratory measure/orders at i, ii or iii**, defined above. For these analyses, we will exclude those that did not have an AP order on randomization date.

Inferential analysis: We will estimate the **odds ratio (OR) of BMI/Laboratory measure/orders observed at i or ii or iii**, between intervention and control. Binary treatment arm assignment will be the only covariate included in the regression model and the estimated coefficient is interpreted as the log-OR of observing BMI/Laboratory measure/orders at i or ii or iii, for an intervention patient vs. a control patient. Patient is the unit of analysis, GEE will be used to account for correlation within provider, and robust standard errors will be calculated to construct a 95% CI around the estimated OR. Our null hypothesis is that the OR is equal to 1, corresponding to no statistically significant difference between BMI/Laboratory measure/orders observed at i or ii or iii, for the treatment arms. We will reject the null hypothesis if the lower bound of the 95% CI is above 1 (increased BMI/Laboratory

Analysis plan for Safety Use of Antipsychotics in Youth (SUAY)

measure/orders in treatment arm) or the upper bound is below 1 (decreased BMI/Laboratory measure/orders in treatment arm). For these analyses, we will exclude those that did not have an AP order on randomization date.

Variables	Definition	Present/Absent

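### Secondary analysis II restricts the BMI and laboratory comparison to patients with a day-0 antipsychotic order, which the intervention alert itself changes, so its odds ratio should not be tested as an intervention effect

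*SAP*

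**What the plan says.** SAP Secondary analysis II fits logistic models for a BMI or laboratory record at baseline (90 days before to 7 days after randomization), at follow-up (day 30 to day 181), and at both. Treatment arm is the only covariate. The coefficient is read as intervention patient against control patient, and the null hypothesis of an odds ratio of 1 is rejected when the 95% interval excludes it. The restriction is repeated for the descriptive summary and the models: "For these analyses, we will exclude those that did not have an AP order on randomization date". The coding follows it: "If no AP orders were made on the randomization date then these variables should be NA". No version with all enrolled patients is planned.

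The protocol describes how the order status arises:

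- Section 7.1, first choice in the intervention alert: "keep/remove the medication entered (default = remove").
- Section 5.2, under the service-order inclusion criterion: "The BPA allows providers to remove the antipsychotic order and still order services".
- Appendix A, a second way into the enrolment log: "The intervention arm provider directly orders a study service (i.e., navigation, bridging therapy, CAP consult) in Epic outside of the medication alert".
- Section 6, for control: "The firing of the control arm medication alert will add the patient to the study enrollment log as a comparison case". A control provider who tries to order a study service is told that the patient is not eligible for it.

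Protocol 3.2 lists the safety-assessment outcome without any restriction to patients with an order.

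**The concern.** An antipsychotic order on the randomization date is not a baseline characteristic. It results from a choice made inside the alert, and the alert differs by arm. Ordering of antipsychotics is also what the intervention is meant to change, since both primary outcomes are measured from orders.

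The exclusion drops intervention patients whose prescriber accepted the default removal. Comparable control patients, whose order stood, remain. If the dropped patients would have been monitored more or less often than the rest, the odds ratio moves away from 1 for that reason alone.

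The baseline outcome shows this most clearly. Its window lies almost wholly before the alert, so a difference there would largely reflect chance or selection. The SAP would nevertheless report it as increased or decreased assessment in the treatment arm. For follow-up laboratory tests a real effect is plausible, because navigators remind families about them (Protocol 7.4), so readers will take the odds ratio as causal. At stake is an unsupported claim that the intervention improved or worsened safety assessment.

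**Working it through.** The plan gives no rate, sample size or power for this outcome, so there is no stated figure to reproduce. The check is an illustration with no true effect on monitoring.

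**From the documents.** Up to 400 patients per arm (Protocol 8.1); two-sided 5% test (95% interval, SAP Secondary analysis II).

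**Assumed.** A share r of intervention patients has the order removed by the alert, and none in control. Monitoring probability is 0.50 in patients whose order stands under either alert and q in those whose order only the intervention alert removes.

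**Restricted analysis.** Intervention patients analysed: 0.50 monitored. Control patients analysed: p = (1 − r) × 0.50 + r × q. The odds of 0.50 are 1, so OR = (1 − p)/p.

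| r | p, q = 0.30 | OR | p, q = 0.70 | OR |
|---|---|---|---|---|
| 10% | 0.48 | 1.08 | 0.52 | 0.92 |
| 20% | 0.46 | 1.17 | 0.54 | 0.85 |
| 30% | 0.44 | 1.27 | 0.56 | 0.79 |

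With q = 0.40 the odds ratios are 1.04, 1.08 and 1.13. With q = 0.50 they are 1.00.

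**False rejection.** This uses a normal test with unpooled variance and no clustering. For r = 20% and q = 0.30, the analysed numbers are 320 and 400. The difference is 0.50 − 0.46 = 0.04 and the standard error is √(0.25/320 + 0.2484/400) = 0.0374, so the probability of rejecting is 18.7%. At r = 10% and 30% it is 8.5% and 33.9%. At q = 0.40 it is 5.9%, 8.3% and 12.0%.

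**Some removal in control.** If a share c = 5% of controls also lacks an order, p = [(1 − r) × 0.50 + (r − c) × q]/(1 − c). With q = 0.30 the odds ratio is 1.135 at r = 20% and 1.235 at r = 30%, with false rejection of 13.3% and 26.8%. The effect shrinks but remains.

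**All enrolled, monitored yes/no.** Both arms then have probability (1 − r) × 0.50 + r × q, so the odds ratio is 1.00 for any r and q, provided the enrolled patients are otherwise comparable.

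**A composite of ordered and not monitored, with no-order patients scored 0.** Intervention probability is (1 − r) × 0.50; control probability is 1 − p. Still with no effect on monitoring:

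| r | OR, q = 0.30 | OR, q = 0.70 |
|---|---|---|
| 10% | (0.45/0.55)/(0.52/0.48) = 0.76 | 0.89 |
| 20% | (0.40/0.60)/(0.54/0.46) = 0.57 | 0.78 |
| 30% | (0.35/0.65)/(0.56/0.44) = 0.42 | 0.69 |

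All six lie further from 1 than the restricted analysis, and all favour the intervention. The composite chiefly re-measures prescribing.

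**The case against.** The restriction has a sensible motive. Metabolic monitoring matters for treated youth; Protocol 7.4 ties the laboratory reminder to having started an antipsychotic; and the SAP, under its predictor of interest, describes the comparison as one of patients initially prescribed the drug. This supports showing the restricted percentages. It does not support testing an unadjusted odds ratio between arms as an intervention effect.

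The enrolled arms are not a clean randomized set either. Providers are randomized, and "Patients are assigned to the study arm of the randomized prescribing provider" only once the alert fires or a service is ordered. Under Protocol 5.5 an alert is cancelled when the drug is de-selected and no support is ordered. Intervention patients can enter by a service order alone, a route that control lacks; excluding those particular patients improves comparability, and the formulas above do not cover them. This stands, so an all-enrolled comparison removes one added layer of selection but not all of it.

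A reader might infer a plain breach of intent-to-treat. Protocol section 3 does say "we will follow an intent-to-treat approach and encouragement trial methods", but the context is collecting outcomes whatever the uptake of components. Protocol 8.2.1 applies the principle to primary analyses, and the SAP's explanation concerns patients who later see a provider in the other arm. The exclusion sits badly with these statements, but the case against it rests on selection.

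The sizes are wholly assumed. The control alert's default is not shown (Appendix B lists titles only), so even the arm difference in removed orders is unknown.

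**Conclusion.** The concern holds for the BMI and laboratory process outcome. The analysis set depends on a status fixed after the alert and altered by the intervention alert, and the planned test treats the result as an intervention effect. The illustrative null odds ratios of 1.08 to 1.27, or 0.92 to 0.79, rest on 10% to 30% removal in the intervention arm, none in control, and monitoring of 30% or 70% in removed patients against 50% in the rest. The bias vanishes if removed patients are monitored like the others.

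Two stronger readings are not supported. One is that the trial's safety monitoring is compromised: the emergency and urgent-care analysis (SAP Secondary analysis I) and the DSMB comparisons (Protocol 10.1) carry no such exclusion. The other is that the result is biased in a known direction or by a known amount: nothing in the documents fixes either.

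**What to change.** 1. Present the restricted percentages, and any restricted odds ratio, as descriptive and non-randomized. Delete the rule that rejects an odds ratio of 1 as an intervention effect in that subset.
2. Report by arm the number of patients without an order on the randomization date, showing separately those who entered only through a service order.
3. Code the monitoring variables for all enrolled patients instead of NA. Add a between-arm comparison of monitored yes/no by assigned arm, with a sensitivity analysis leaving out patients who entered only through a service order outside the alert.
4. If a composite of ordered and not monitored is shown, keep it supplementary and label it as combining prescribing with monitoring; it should not be the main test.

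The cost is SAP wording and a recode; the SAP's variable table marks the monitoring variables as absent. If the analysis has already been run, the labelling, the counts and the added comparison can still be supplied. The downside is that monitoring means less in patients without an order, and the all-enrolled set keeps some post-alert enrolment selection, so the two results must be read together.
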